The target patient population consists of 388 outpatients affected by hereditary haemoglobinopathies requiring chronic transfusion and chelation, randomized 1:1 in two groups of 194 patients each to ensure 310 evaluable patients. Chelation naïve and not naïve patients aged from 1 month to less than 18 years will be recruited. A staggered approach will be applied to patients aged less than 6 years (10% of the total sample), which will be recruited after results from the PK Study (Study DEEP-1, EudraCT n. 2012-000658-67) will be available.

Experimental arm: patients administered with DFP at 75-100 mg/kg/day for seven days per week. In patients aged less than 6 years the dose will be defined according to the results of the PK Study (Study DEEP-1, EudraCT n. 2012-000658-67). DFP daily dose will not exceed 100 mg/kg.

Control arm: patients administered with DFX at 20-40 mg/kg/day as recommended by the currently approved European SmPC (last update 10/08/2011). DFX daily dose will not exceed 40 mg/kg.

Details on the starting dose and subsequent dose adjustments are reported in **Section 6**.

The **treatment duration** for both groups is 12 months.

4.1Non-inferiority margin

This study is designed to demonstrate the **non-inferiority** of a new liquid DFP (80 mg/mL) formulation in comparison with DFX in terms of percentage of successfully chelated patients as described in **Section 4.3**.

DFP will be declared non inferior to DFX if the lower limit of the 95% confidence interval for the difference in the proportion of successful chelation in the two groups is above -12.5%. The choice of this margin is based on clinical considerations starting from the available evidences for the effects of DFX at both ferritin and cardiac levels. For details please refer to **Section 11**.

4.2Choice of comparator

DFP will be compared to the oral chelating agent DFX. The rationale for comparing two oral chelators derives from the recent literature data reporting that oral chelating agents currently represent the most widespread adopted therapy in the paediatric age, due to good compliance, improved QoL and reduced burden of the disease (Ceci A et al, 2011).

4.3Primary endpoint

The primary endpoint will be the measure of treatment efficacy defined as the percentage of patients successfully chelated, as assessed by serum ferritin levels (in all patients) and cardiac MRI T2* (in patients above 10 years of age able to have an MRI scan without sedation).

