The choice of this composite endpoint allows the feasibility of the trial in the entire paediatric population and provides an up to date approach to the evaluation of the global iron accumulation in paediatric transfusion-dependent patients. In addition the use of a composite endpoint (rather than an alternative one) allows avoiding multiplicity while adequately characterising (total body iron load and in the heart) the beneficial effect of treatments.

Each component of the composite endpoint will be considered for secondary analyses with the intent to clarify the interpretation of the composite. For such analyses no adjustment for multiplicity will be foreseen (see **Section 11.2**).

Based on the above defined composite endpoint, non inferiority is established if the lower limit of two sided 95% confidence interval of the difference in success rate is above - 12.5%. The choice of this margin is based on clinical considerations starting from the available evidences for the effects of DFP and DFX on ferritin levels and cardiac iron load.

In details, the percentage of expected success for DFX and DFP measured as change from baseline to 1 year treatment is summarised in the following **Table 6**:

Table 6: Success rates for DFP and DFX

Serum ferritin levels	76% (95%CI: 63.6-88.5) DFP mean dose 66.4 mg/kg/day (Addis A et al, 1999) Paediatric population included in the meta-analysis but not analysed separately.	57% (95%CI: 50.7-63.3) DFX used at 20-30 mg/kg/day (Taher A et al, 2009) 75 adult and 162 paediatric patients
Cardiac MRI T2*	66% Higher percentage in splenectomised patients (Pennell DJ et al, 2006) 29 adults	69.5% in patients with moderate-to-mild baseline cardiac iron load (≥ 10 to <20 ms) DFX mean dose 33.1 \pm 3.7 mg/kg/day (Pennell DJ et al, 2010) 72 adult and 29 paediatric patients

Pooling together these findings, the expected percentage of success in the composite endpoint is assumed to be equal to 65% and 67.5% for DFX and DFP, respectively. The non inferiority margin of 12.5% has been considered to be a good estimate of an achievable lower bound of the true difference between the DFP and DFX.

Other secondary objectives include the evaluation of treatment efficacy in terms of liver iron concentration, the assessment of treatment safety and tolerability profiles, healthcare resources utilisation and patient global assessment and the analysis of the relationship of the demographic covariates and the disposition of DFP.

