11.2 Study population

Intent to treat population

For the intent to treat (ITT) analysis all patients that have been randomized and start therapy will be included.

Per protocol population

Patients in the per protocol (PP) population for the primary efficacy analysis (PP1) are those that have received the study drugs and for whom the composite endpoint is available at baseline and after 1 year treatment, without major protocol violations.

For the secondary efficacy evaluation assessed as non-inferiority of DFP to DFX in terms of serum ferritin levels the PP population (PP2) includes only patients for whom the measure of serum ferritin is available at baseline and after 1 year treatment.

For the secondary efficacy evaluation assessed as non-inferiority of DPF to DFX in terms of successfully chelated patients according to cardiac MRI T2* the PP population (PP3) includes only patients for whom the measure cardiac MRI T2* is available at baseline and after 1 year treatment.

Safety population

The population for the safety and tolerability analysis will include all patients having received at least one dose of study medication.

PK and PKPD population

The population for the pharmacokinetic and subsequent exploratory analyses (e.g. correlation between systemic exposure and ferritin levels) will include patients who have received the investigational drugs throughout the duration of the study (i.e., 1 year) and have had a blood sample collected for the assessment of drug concentrations in plasma.

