In the last years, the role of cardiac MRI T2* in the management of patients affected by hereditary haemoglobinopathies has been highlighted. Findings are available for the adult population, more limited experience is reported in children. Despite the importance of early detection of cardiac siderosis, MRI is difficult to perform in the paediatric population and it is usually uninformative in younger children (namely less than 10 years) due to late iron accumulation in the heart.

As a consequence, cardiac MRI T2* will be analysed as additional secondary measure of treatment efficacy in the subgroup of patients (over 10 years) for which the scan is available. It will be analysed as binary variable (successfully/unsuccessfully chelated patient according to the criterion 4.3.1 in Section 4.3) as part of the composite endpoint as well as according to its quantitative nature.

Due to the paucity of paediatric data on cardiac MRI T2*, descriptive statistics will be calculated and used to support efficacy conclusions. Descriptive measures will be listed by visit and treatment and characterised by frequency and percentage or mean, standard deviation, median, and quartiles.

However, considering the importance of improving knowledge on iron overload at the heart level in the paediatric population, a test for non inferiority of DFP to DFX in terms of cardiac MRI T2* (successfully/unsuccessfully chelated patient according to the criterion 4.3.1 in Section 4.3 Primary endpoint) will be performed whenever MRI evaluation will be available in at least 60-70% of the evaluable population. See section 11.3 different scenarios (non inferiority margins and sample size) related to this secondary efficacy assessment. The population for this analysis is the PP3.

Efficacy measured through MRI liver iron concentration

Iron overload in the liver compartment will be assessed as additional secondary measure of efficacy. LIC changes within one year will be evaluated in terms of percentage of successfully chelated patients according to the success criterium described in section 4.4.1 Secondary endpoints. LIC absolute values will be also analysed.

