11.12 Sample Size and power considerations

Primary efficacy objective

Assuming type I and type II errors of 0.025 and 0.20, respectively, and a one-sided test, and under the assumptions that the expected proportion of subjects declared treatment successes in the DFX arm is 65%, and the expected proportion of subjects declared treatment successes in the DFP arm is 67.5% a sample size of 310 subjects, randomized in a 1:1 ratio to DFP or DPX will yield 80% power to demonstrate non-inferiority of DFP versus DFX. Taking into account a possible dropout rate of about 20% a total enrolment of 388 patients aged from 1 month to less than 18 years are expected to be included in the trial.

Secondary efficacy objective

Sample size requirements for the secondary efficacy objectives (non-inferiority in terms of ferritin levels and cardiac MRI T2*) are provided in the following.

Based on published literature, testing for non-inferiority is appropriate also when comparing DFP to DFX efficacy in terms of serum ferritin levels. In this case, considering a hypothesis testing on the continuous measure, a non inferiority margin of 400 ng/ml is considered a reliable estimate of the true allowed maximum difference between the IMPs in order to assume DFP to be non-inferior to DFX in controlling iron overload in patients affected by hereditary haemoglobinopathies. The standard deviation of the differences is available by pooling findings from paediatric studies conducted in Europe and outside (El Alfay M et al., 2010), and a reliable and conservative estimate can be 1000 ng/mL.

On these assumptions, 310 evaluable patients are sufficient to provide at least 90% power to demonstrate non inferiority of DFP to DFX, assuming a type I error of 0.025 and a one-sided test.

When considering efficacy in terms of cardiac MRI T2*, less reliable estimates of treatment efficacy are available, especially in the paediatric population. However, there are no reasons for not assuming at least a non inferiority of DFP to DFX, considering also the known beneficial effects of DFP at the cardiac level. Based on the limited published figures of cardiac MRI T2* in the paediatric population and taking into account adult data, some plausible scenarios of sample sizes and related powers are provided in the following **Table 7**, assuming a type I error of 0.025 and a one-sided test. Detailed power curves will be provided in the statistical plan.

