Table 7. Sample size and power on cardiac MRI T2* (percentage of successfully chelated patients)

DFX/DFP Success (%)	65/70	65/70	70/75	70/75
Non inferiority margin (%)	-12.5	-10	-12.5	-10
Power (%)	80	75	80	75
n (per group)	112	135	102	123

On these calculations, a test for non inferiority in terms of percentage of successfully chelated patients according to the criterion 4.3.2 as defined in Section 4.3 Primary endpoint is considered feasible and supported by an adequate power whenever cardiac MRI T2* is available in about 60-70% of the evaluable population.

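### At 60-70% of 310 evaluable patients, the cardiac T2* non-inferiority test mostly falls short of Table 7's stated power, and no T2* margin is fixed

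*Combined protocol and SAP*

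**What the plan says.** Section 4 sets the planned numbers: 388 patients, "randomized 1:1 in two groups of 194 patients each to ensure 310 evaluable patients", which is 155 evaluable per arm.

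Section 11.6 makes description the default for cardiac T2*: "descriptive statistics will be calculated and used to support efficacy conclusions". It then adds a formal non-inferiority test on T2* success that "will be performed whenever MRI evaluation will be available in at least 60-70% of the evaluable population". For the margin it only refers the reader elsewhere: "See section 11.3 different scenarios (non inferiority margins and sample size) related to this secondary efficacy assessment". Section 11.3 has no such scenarios; they are in Table 7, Section 11.12.

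Table 7 assumes a one-sided type I error of 0.025 and lists four scenarios:

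| DFX/DFP success (%) | Margin (points) | Power (%) | n per group |
|---|---|---|---|
| 65/70 | -12.5 | 80 | 112 |
| 65/70 | -10 | 75 | 135 |
| 70/75 | -12.5 | 80 | 102 |
| 70/75 | -10 | 75 | 123 |

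From this table Section 11.12 concludes that the test "is considered feasible and supported by an adequate power whenever cardiac MRI T2* is available in about 60-70% of the evaluable population". The analysis set is narrow: "the PP population (PP3) includes only patients for whom the measure cardiac MRI T2* is available at baseline and after 1 year treatment" (Section 11.2). Section 11.12 also says: "Detailed power curves will be provided in the statistical plan".

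**The concern.** The statement about power is offered as a consequence of Table 7, so it should follow when the percentage is turned into patients. It does not: 60-70% of 155 per arm is 93 to 108, whereas the table asks for 102 to 135.

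Two gaps add to this. First, the trigger is a range. If scans are available in 65% of patients, an instruction of at least 60-70% does not say whether the test is run. Second, the margin is left open. The -12.5 points in Section 11.1 are tied to the composite ("Based on the above defined composite endpoint, non inferiority is established if the lower limit of two sided 95% confidence interval"), ferritin has its own margin of 400 ng/mL, and T2* has only scenarios. A lower confidence limit between -12.5 and -10 would then support either conclusion, and in an open-label trial that choice should not be left until the data are in.

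The lower end of the range can occur. Scans depend on age 10 or over and no need for sedation (Section 4.4.2), and Section 6.6 fixes no numbers per age group.

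**Working it through.** **Inputs.** Success rates, margins, powers and n come from Table 7; one-sided type I error 0.025 from Section 11.12; 310 evaluable at 1:1 from Section 4. The interval with unpooled variance is given in Section 11.6 for the primary test and is assumed here for T2*.

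**1. Reproduce Table 7.** Let V = p1(1-p1) + p2(1-p2) and d = (DFP rate - DFX rate) + size of the margin. Then n per group = V × (1.960 + z_power)² / d².

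- 65/70: V = 0.2275 + 0.2100 = 0.4375. At -12.5, d = 0.175 and n = 112.1. At -10, d = 0.150 and n = 135.0.
- 70/75: V = 0.2100 + 0.1875 = 0.3975. At -12.5, n = 101.9. At -10, n = 122.6.

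Table 7 is sound. The fault lies in the step from n to a percentage.

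**2. Turn the trigger into patients.** 0.60 × 310 = 186, or 93 per arm. 0.70 × 310 = 217, or about 108 per arm. As shares of 155, Table 7's counts are 112/155 = 72%, 135/155 = 87%, 102/155 = 66% and 123/155 = 79%. Only one lies inside 60-70%.

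**3. Power at the trigger.** Power = Φ(d / √(V/n) - 1.960). Example, 65/70 at -12.5 with n = 93: √(0.4375/93) = 0.0686; 0.175/0.0686 - 1.960 = 0.592; Φ(0.592) = 72.3%.

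| Scenario | Stated | 93 per arm (60%) | 108 per arm (70%) |
|---|---|---|---|
| 65/70, -12.5 | 80% | 72.3% | 78.5% |
| 65/70, -10 | 75% | 59.0% | 65.4% |
| 70/75, -12.5 | 80% | 76.3% | 82.2% |
| 70/75, -10 | 75% | 63.1% | 69.6% |

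Exact binomial enumeration of the same interval rule agrees: 72.3, 58.8, 76.4 and 63.2% at 93; 78.7, 66.0, 82.3 and 69.9% at 108.

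**4. Evaluable total needed for Table 7's n.** This is 2n divided by the scan share, rounded up. In column order: 374, 450, 340 and 410 at 60%; 320, 386, 292 and 352 at 70%.

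**5. What the open margin is worth.** The probability that the lower limit falls between -12.5 and -10 is the power at -12.5 minus the power at -10. At 93 per arm it is 72.3 - 59.0 = 13.3% (65/70) and 76.3 - 63.1 = 13.2% (70/75). At 108 it is 13.1% and 12.7% (from unrounded powers). For example, at 93 per arm with 65% success on DFX, an observed difference between about +1.2 and +3.5 points in favour of DFP passes at -12.5 and fails at -10.

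**The case against.** The strongest reply is that adequate power is never defined, and that Table 7 itself accepts 75% in two columns. At -12.5, the only margin that the protocol adopts for a success proportion, 75-80% power needs about 99 to 112 per arm (65/70) or 90 to 102 (70/75). That is 64-72% or 58-66% of 155, not far from the stated range. This part stands: at -12.5 the shortfall is moderate, and at 70% it is a near miss (78.5%) or none (82.2%). But the reading pairs -12.5 with a power that the table gives only for -10, leaves 65/70 at 72.3% at the 60% floor, and ignores both -10 columns.

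A second reply is that 310 is a planned minimum. Section 11.13 expects little missing data, Section 9 allows additional enrolment, and no analysis set in Section 11.2 is called evaluable. On all 388 enrolled, 60-70% would be 116 to 136 per arm, close to Table 7, so the percentages may have been worked out on that number; this is only an inference. Both passages say evaluable, however, and the T2* set needs scans at baseline and at one year. Even on 388, both -10 columns miss at 60% (68.7% and 72.8% against 75%), although all four are met at 70%.

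Third, a separate statistical plan is announced and is not in the text reviewed. The announcement covers power curves. It promises neither a margin nor a corrected trigger.

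Finally, this is a conditional, supportive test with description as the default. Low power makes an inconclusive result more likely; it does not create a false claim of non-inferiority. That limits the weight of the point but does not make the sentence correct.

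**Conclusion.** The concern holds. The claim of adequate power at 60-70% of the evaluable population does not follow from Table 7. At 60% of 310, under the table's own rates, the test would fail to show non-inferiority in 24-28% of trials at -12.5 (20% stated) and in 37-41% at -10 (25% stated). At 70%, the -12.5 columns are met or nearly met, and the -10 columns remain 5 to 10 points short.

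Separately, the unchosen margin leaves the conclusion open in about 13% of trials.

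These figures rest on 310 evaluable patients split equally, Table 7's success rates, the normal-approximation interval, and each column's stated power as the benchmark. The sample size and the primary analysis are not affected.

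**What to change.** Choose one T2* margin and justify it. Then, in Sections 11.6 and 11.12, do one of the following:

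- Replace the range with one minimum count per arm in the PP3 set, naming the denominator: 112 (72% of 155) for 65/70 at -12.5; 135 (87%) for 65/70 at -10; 102 (66%) for 70/75 at -12.5; or 123 (79%) for 70/75 at -10.
- Keep the range, state the power that it gives on 310 evaluable (59-76% at 60%, 65-82% at 70%), and drop the claim of adequacy where the target is missed.

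Below the trigger, report the difference with its 95% confidence interval descriptively and make no non-inferiority claim. Correct the pointer in Section 11.6 from 11.3 to 11.12. The announced power curves could usefully include a true difference of +2.5 points and equal rates.

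The cost is wording in two sections. With a single count, the formal test may not be triggered, most plausibly at 135 per arm, and T2* would then remain descriptive. The planned 310 evaluable and 388 enrolled do not change.

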11.13 Handling of missing data

A negligible amount of missing data is expected in this study because the patient population under study (patients affected by haemoglobinopathies requiring chronic transfusion and chelation therapy), and their parents, are accustomed to routine close monitoring in clinical visits, are used to frequent lab tests and comply with uncomfortable examinations (MRI), and are generally willing to participate in trials that may lead to increasing the availability of treatments. Moreover, the estimated treatment effect is not expected to be importantly biased in favour of the experimental treatment due both to the choice of the comparator and of the primary endpoint.

DFX is an oral chelator as DFP, and its compliance is expected to be comparable to that of DFP, or even better taking into account the once a day administration.

The completeness of the data that will allow the estimate of the primary endpoint (percentage of successfully chelated patients) is expected to be high due to the type of patients and condition.

Finally, patients who prematurely discontinue the trial for any reason will be considered treatment failures.

Assuming the worst scenario for incomplete data in order to provide conservative estimates for the trial results, the imputation of missing data will only apply to missing data because of a missing visit. This will affect the trend analysis for the secondary evaluation on serum ferritin levels. In this case, Linear Mixed Models (LMM) will be used as imputation method for missing data.

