11.6 Efficacy evaluation

Primary efficacy

The primary efficacy evaluation will be based on a treatment success rate defined in Section 4.3 Primary endpoint. The primary analysis will be based on the PP1 population.

In addition, an ITT analysis will be performed to corroborate the findings. If no composite endpoint is estimable at 1 year treatment (unavailability of serum ferritin and/or MRI determination either at baseline or after 1 year treatment), the subject is considered a treatment failure in the ITT analysis. Non-inferiority will be assessed based on the two sided 95% confidence interval $[\delta_L, \delta_U]$ of the difference $\delta = p_1 - p_2$, being p_1 and p_2 the proportion of success in the n_1 and n_2 patients randomised to DFP and DFX arms, respectively. Non-inferiority will be claimed if δ_L is greater than -0.125. The two sided 95% confidence interval for δ will be estimated based on asymptotic normal approximation for the difference of two binomial probabilities as follows:

$$(p_1 - p_2) \pm Z_{1-\alpha/2} \sqrt{Var(p_1 - p_2)}$$

where Z_γ is the γ^{th} percentile of the standardised normal distribution and

$$Var(p_1 - p_2) = p_1(1 - p_1)/n_1 + p_2(1 - p_2)/n_2$$

If non-inferiority of DFP to DFX is established based on the PP1 population and the confidence interval for the null hypothesis of non-inferiority based on the ITT population is similar or the percentage of success for DFP is greater than that of DFX in magnitude, the hypothesis that DFP is superior to DFX in terms of the defined success criteria will be tested at the one-sided alpha level of 0.025. Superiority testing will be based on the ITT population. The rationale for superiority is justified by the known beneficial effects of DFP at the cardiac level.

Secondary efficacy

Efficacy measured through serum ferritin levels

Serum ferritin will be analysed as secondary measure of treatment efficacy. Serum ferritin is a well validated and clinically widespread surrogate measure of iron load, highly correlated with iron in the liver. It represents an easy to assess parameter in the paediatric population.

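### Scoring missing outcomes as failures in both arms is not reliably conservative for non-inferiority, so the ITT analysis supports the per-protocol result less than it appears to

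*Combined protocol and SAP*

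**What the plan says.** Section 11.6 makes PP1 the primary analysis. Section 11.2 limits PP1 to patients with the composite available at baseline and at one year and no major violation, so a missing outcome removes a patient from PP1. The ITT analysis is added to corroborate. There, if ferritin and/or MRI is unavailable at either time point, "the subject is considered a treatment failure in the ITT analysis". The rule is the same in both arms and does not depend on why the value is missing.

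Two further rules name no analysis set. Section 9 counts patients withdrawn early from treatment as failures, and Section 11.13 does the same for anyone who discontinues the trial, whatever the reason. The next sentence of Section 11.13 opens with "Assuming the worst scenario for incomplete data in order to provide conservative estimates for the trial results" and goes on to restrict imputation to missed visits, which it ties to the secondary ferritin trend analysis (linear mixed models).

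On the amount of missing data, Section 11.13 states "A negligible amount of missing data is expected in this study", while Section 11.12 sizes enrolment with the words "Taking into account a possible dropout rate of about 20" (per cent). Apart from PP1 (complete cases) and ITT (failure scoring), no handling of missing data is described for the binary primary endpoint.

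**The concern.** In a superiority trial, counting missing outcomes as failures in both arms usually works against the claim, because it pulls the arms together. In a non-inferiority trial with a fixed absolute margin, the same pull works in favour of the claim. If DFP were truly worse than DFX by exactly the margin, failure scoring would make the observed gap smaller than the margin, and the ITT interval would clear -12.5 points more often than it should.

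The rule also covers losses that say little about treatment: a missing baseline scan, a missed month-12 scan, or loss to follow-up. Section 20 itself acknowledges logistic difficulty for patients who must travel to another centre for MRI. What is at stake is the value of the ITT analysis as a check on PP1. A reader told that both analyses agree would give the agreement more weight than it deserves.

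**Working it through.** **Inputs.** One-sided 0.025 and 80% power; success 65% (DFX) and 67.5% (DFP); 310 evaluable patients; about 20% dropout (all Section 11.12). Margin -12.5 points and a normal-approximation interval with unpooled variance (Section 11.6). 194 randomised per arm (Section 4). The documents give no missingness by arm, so the missing shares d below are assumptions; 20% borrows the plan's dropout figure.

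**1. The plan's own figure.** n per arm = (1.960 + 0.842)² × (0.65×0.35 + 0.675×0.325) / (0.025 + 0.125)² = 7.849 × 0.446875 / 0.0225 = 155.9, so 156 per arm or 312 in total, against 310 stated. Power at 155 per arm is 79.8%. 310/0.80 = 387.5, rounded up to 388. The design reproduces to within two patients.

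**2. Effect of failure scoring.** With equal missingness d unrelated to outcome, the observed rate is p(1 - d) in each arm, so the observed difference is (1 - d) times the true one. At the margin (65% v 52.5%) with d = 20%: DFX 0.65×0.8 = 52%, DFP 0.525×0.8 = 42%, difference -10.0 points.

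**3. False-pass rate of the ITT test alone, 194 per arm.** At d = 20%, SE = √[(0.42×0.58 + 0.52×0.48)/194] = 0.0504, and Φ((-0.100 + 0.125)/0.0504 - 1.960) = Φ(-1.464) = 7.2%. Exact binomial enumeration of the same interval gives:

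| d, both arms | Observed difference (points) | Probability that lower limit exceeds -12.5 |
|---|---|---|
| 0% | -12.5 | 2.6% |
| 5% | -11.9 | 3.4% |
| 10% | -11.25 | 4.2% |
| 20% | -10.0 | 7.0% |
| 30% | -8.75 | 11.7% |

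**4. Unequal missingness.** The true rates are again at the margin. For example, DFP 22% / DFX 18% gives 0.525×0.78 - 0.65×0.82 = -12.35 points.

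| Missing DFP / DFX | Observed difference (points) | False-pass rate |
|---|---|---|
| 25% / 15% | -15.9 | 0.4% |
| 22% / 18% | -12.35 | 2.6% |
| 18% / 22% | -7.65 | 15.6% |
| 15% / 25% | -4.1 | 37.8% |

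At 20% average missingness and a gap g (DFP minus DFX), the observed difference is -0.100 - 0.5875g. It equals -0.125 when g = 0.025/0.5875, about 4.3 points. Above that gap the rule is conservative; below it, it is not.

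**5. PP1 and ITT together.** One million simulated trials at the margin, 20% equal missingness unrelated to outcome: PP1 passes falsely 2.5%, ITT 7.0%, both 2.1%. When PP1 passes falsely, ITT agrees in 0.0211/0.0249 = 85% of cases. Agreement is similar at 5% and 10% missing (87% and 84%), so it should not be put down to dilution alone.

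**6. If the missing patients really are failures.** Take true overall rates of 65% v 52.5% and 20% missing, half of them true failures and half like completers. The observed rates are 0.65×0.8/0.9 = 57.8% and 0.525×0.8/0.9 = 46.7%, a difference of -11.1 points and a false-pass rate of about 4.4%. If all are true failures, the complete-data rate of 2.6% returns.

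**The case against.** The strongest objection is that the trial's claim rests on PP1. Patients with missing outcomes leave PP1 and are not failed, and Section 11.6 speaks of non-inferiority being established on that population. A reader might infer from the 7.0% that the trial's own false-claim rate is raised to that level. The documents do not support this: with missingness unrelated to outcome, PP1 holds about 2.5%. The inflation would reach the primary test only if the failure rules of Sections 9 and 11.13 were also applied there. The text leaves that open, but PP1's requirement for a one-year value points the other way.

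A reader might also infer that the plan calls its ITT rule conservative. Section 11.6 never does. The phrase in Section 11.13 belongs grammatically to missed-visit imputation for the ferritin trend. The link to failure scoring is suggested by the sentence before it but not stated.

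Third, withdrawal reasons in Section 9 include unsatisfactory effect and adverse events requiring a change of chelation. Such patients may be genuine failures. If discontinuation is part of the endpoint, the diluted difference is the target and there is no inflation for that target. Step 6 shows how far this reduces the effect. It does not cover a missing baseline scan or a missed month-12 scan.

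Fourth, the direction depends on which arm loses more patients (step 4). That stands, and it is why the rule cannot be presumed conservative either.

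PP1's protection has its own condition. As an illustration, take 20% missing per arm, true rates at the margin, and missing patients who would have succeeded 40% of the time on DFP and 65% on DFX. PP1 then passes falsely 8.1%, ITT 15.9% and both 6.9%. In such a case ITT is the check one would look to, and it does not help.

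**Conclusion.** The concern holds for the ITT analysis as a corroborating check; it is not a defect shown in the primary test. Under equal missingness unrelated to outcome, the ITT test alone has a one-sided false-pass rate of about 4.2% at 10% missing and 7.0% at 20%, against 2.5% nominal. Under the same assumption PP1 stays at about 2.5%, or 2.1% if both must pass. With a modest imbalance between arms the ITT figure ranges from 2.6% (DFP 22% / DFX 18%) to 15.6% (18% / 22%).

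These sizes rest on true rates exactly at the margin, all 194 per arm starting therapy, and a missing share that the documents do not give. The 20% is a dropout figure, not a count of missed assessments, and the share due to missed scans alone cannot be derived from the plan. The stronger conclusion, that the rule always favours DFP, does not follow. The supportable one is that failure scoring is not reliably conservative here, and that agreement of ITT with PP1 is weaker support than it looks.

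**What to change.** - In Sections 9, 11.6 and 11.13, state which analysis set each failure rule applies to.
- Do not describe failure scoring as conservative for non-inferiority; confine the phrase in Section 11.13 to the ferritin trend, or drop it.
- Keep failure scoring for treatment withdrawals if withdrawal is meant to be part of the endpoint, and say so.
- For outcomes missing for other reasons (missed scan, missing baseline, loss to follow-up), prespecify an ITT sensitivity analysis by multiple imputation. Add a tipping-point table by arm that includes imputation under the non-inferiority null (DFP at the DFX rate minus 12.5 points).
- Report missingness by arm and reason, and show this analysis beside PP1 and ITT as a robustness check.

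It should not be a mandatory gate. At the design rates with 20% missing, requiring the null-imputation analysis to pass would cut power to roughly 63%, against about 80% for PP1, and so undo the sample size.

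The cost is a little more analysis work and no new patients or visits. The downside for the sponsor is that a non-inferiority claim may have to be reported as less robust.
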